5.2 Safety Evaluation

Subject safety will be monitored by adverse events reporting. As this study is not greater than minimal risk serious adverse events are not anticipated.

6 STATISTICAL CONSIDERATIONS

6.1 Primary Endpoint

For phase 1, the primary endpoint will be the qualitative interview responses used to inform texts and survey for phase 2. For phase 2, the primary endpoints will be acceptability and feasibility of the intervention. To determine feasibility and acceptability of the intervention, we will assess the number of participants who complete the daily text messages and query participants on their overall satisfaction measure (5-point Likert scale) with their intervention group and provide survey questions regarding likes and dislikes concerning the intervention group they received following the intervention period.

6.2 Secondary Endpoints

Secondary outcomes will be explored in phase 2 to determine the differences in reading frequency, the home reading environment, parenting stress, and child language and socio-emotional development at 2 months.

6.3 Control of Bias and Confounding

Randomization and allocation concealment are the primary means of avoiding bias. Analytic strategies will also be used to control for residual confounding: (1) Stratification will control for imbalance not controlled by design. (2) Additional potential confounders will be evaluated for any residual association with treatment and included in model as needed. (3) Post randomization effects: The primary source of bias will arise after randomization from dropout and loss to follow-up. To address this problem and avoid missing data, we shall implement the following measures: (a) incentives to each family to complete the study, (b) collection of multiple contact numbers and tracking of changes, and (c) contact all randomized participants, even if they do not continue with their clinical contacts.

6.4 Statistical Methods

6.4.1 Baseline Data

Descriptive statistics for demographic, home reading environment, and parenting stress measured at baseline will be examined across the three groups to assess the success of the randomization.

6.4.2 Sample Size Justification

The planned sample size for Phase 1 is 10 participants and for Phase 2 is 15 participants per group. Ten participants in phase 1 will be sufficient to provide information to develop coaching tips and identify the main obstacles to parent child reading in phase 2. Our target sample size for phase 2 is 45 participants with 15 participants per group. This sample size is based on the availability of funds and ability to complete the study within a 1 year time period.. These sample sizes were determined to adequately assess feasibility and acceptability. As a pilot study, a power calculation is not necessary.

6.4.3 Analysis of Primary Outcomes of Interest

6.4.3.1 Specific Aim 1

Primary outcomes:

To determine the feasibility of each group of the intervention, we will assess the proportion of participants who receive and report a daily reading behavior each week across all groups, the proportion of participants who access coaching content in group 2 & 3, and the proportion of participants who participate in the weekly lottery in group 3. To determine acceptability of the intervention, we will assess the number of participants who opt out of the daily text messages and query participants on their overall satisfaction (5-point Likert scale) with their intervention group and provide survey questions regarding likes and dislikes concerning the intervention group they received following the intervention period. The survey questions at the end of phase 2 will be based on input from the rapid-cycle design process of phase 1 interviews. Differences in weekly reading frequency and satisfaction scores between groups will be assessed using standard inferential statistics and intention-to-treat analysis. Survey question responses will be assessed using qualitative methods in which codes will be developed and emerging themes identified by consensus of investigators using NVivo software.

Secondary outcomes:

To explore differences in reading frequency, the home reading environment, parenting stress, and child language and socio-emotional development, we will examine differences in mean weekly reading frequency, mean changes in StimQ Read Subscale scores and PSI-SF scores, and mean CDI and DECA scores between groups using standard inferential statistics and intention-to-treat analysis. In addition, effect sizes will be computed to assess differences between Group 1 and each of the other 2 groups and to power future studies.

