After conducting the rapid-cycle design for phase 1, forty-five eligible children and their parents will be consented and enrolled in the study. In the event that the baseline visit cannot be completed in-person an alternative method of obtaining informed consent electronically through REDCap will be used. Following informed consent and completion of baseline surveys, participants will be stratified by site and randomized 1:1:1 to receive one of the 3 AH interventions for an 8-week duration. Using a similar recruitment strategy, we were able to successfully recruit 120 (81%) of 148 low-income infants and their parents who were approached for the aforementioned study on early literacy promotion.

Group 1 will consist of daily text messages on shared reading, which will be sent to participants using the Way to Health Platform. Participants will be asked to reply to the text message on daily shared reading activities including the titles of books and time spent reading. Group 2 will consist of Group 1 plus personalized coaching. Personalized coaching content will be made available to participants through links in the text messages and will provide comparisons of their reading frequency with that of other participants. These comparisons will be blinded to preserve confidentiality. Finally, Group 3 will consist of Group 2 plus availability of a weekly lottery. Group 3 participants who report back that they read on a particular day will be entered into a weekly drawing to receive \$20. Each reported daily reading behavior will provide a single lottery entry so that participants who report they read all 7 days in a given week will have 7 entries in the weekly drawing.

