3.1.3 Randomized Trial

All participants across groups will be asked to report on daily reading behaviors by replying to daily text messages. In addition, participants will be asked to complete study measures using a RedCap survey at baseline and following the 8-week intervention period. Responses to daily reading text messages will be provided by the Way to Health platform and will be assessed as the mean overall number of days/weeks of reading for each group. Participants will also be provided with an opt out of the daily text messages option if they no longer desire to receive daily text messages. Participants will be queried at follow-up on their overall satisfaction (5-point Likert scale) with their intervention group and asked to answer survey questions regarding likes and dislikes concerning the intervention group they received following the intervention period. The survey questions at the end of phase 2 will be based on input from the rapid-cycle design process of phase 1 interviews.

At baseline, parents will complete a measure of demographics (child and parent age, race/ethnicity, sex, highest education completed, and family income category) (see Appendix 2). To explore differences in the home reading environment, parents will complete the Read subscale of the StimQ, a validated 14-item parent report measure of the home reading environment, at baseline and follow-up.²³ To explore differences in parenting stress, participants will complete the Parenting Stress Index-short form (PSI-SF), a validated 36-item parent report of parenting stress, at baseline and following the 8-week intervention in order to assess changes.²⁴ Finally to explore differences in child language and socio-emotional development, parents will complete at follow-up the MacArthur Communicative Development Inventory (CDI), a validated parent-report scale of early language development, and the Devereux Early

Childhood Assessment (DECA), a validated 33-item parent report of socio-emotional problems.^{25,26}

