3.4.1 Inclusion Criteria

Parent who:

- 1) Have an infant aged 6-24 months
 - 2) Have access to a smart phone with text messaging capabilities
-

- 3) Have completed an informed consent

Children who:

- 4) Are aged 6-24 months old

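### StimQ-Read and PSI-SF are compared as mean changes with no baseline covariate named, and the only stated rule for adding covariates is chance association with treatment, not prognostic value

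*Combined protocol and SAP*

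**What the plan says.** Section 3.1.3 collects "the Read subscale of the StimQ, a validated 14-item parent report measure of the home reading environment, at baseline and follow-up", and PSI-SF at the same two times. CDI and DECA are collected at follow-up only. Section 6.4.3.1 compares the groups on "mean changes in StimQ Read Subscale scores and PSI-SF scores, and mean CDI and DECA scores between groups using standard inferential statistics". It adds that effect sizes for Group 1 against each of the other groups will help to power later studies. No model, baseline score or other covariate is named. Section 6.4.1 gives baseline scores only a descriptive role, as a check on the randomisation.

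The covariate rule is in section 6.3. Item (1) says "Stratification will control for imbalance not controlled by design". Item (2) says "Additional potential confounders will be evaluated for any residual association with treatment and included in model as needed". There is no candidate list, threshold or prognostic criterion. Section 3.1.2 says "participants will be stratified by site and randomized 1:1:1", but nothing says how site enters these comparisons. Child age is available, since "parents will complete a measure of demographics (child and parent age, race/ethnicity, sex, highest education completed, and family income category"), and the eligible children "Are aged 6-24 months old". Age is not named as a covariate for any outcome.

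**The concern.** Subtracting the baseline score uses it with a fixed coefficient of one. Regression on baseline estimates the coefficient, and is usually more precise unless baseline and follow-up are very highly correlated.

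The rule in 6.3 item (2) does not secure this adjustment. After concealed randomisation, an association between a baseline variable and arm is chance. A rule keyed to it lets the model depend on which imbalance happened to appear. It gives no weight to whether the variable predicts the outcome. Without a list or threshold, two analysts following the plan could fit different models to the same data.

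The stake is the precision of the effect sizes meant to inform later trials. With 15 per arm these are imprecise already, and the information that could tighten them is already being collected.

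**Working it through.** **Inputs.** Section 6.4.2 gives 15 per group and 45 in all; 3 × 15 = 45 agrees. It gives no alpha, power, effect size or SD, so there is no power figure to reproduce. The baseline-to-follow-up correlation r is not in the documents and is varied. The only related figure is the StimQ test-retest ICC of 0.93 in section 5.1.2, which is not stated for the Read subscale or for an 8-week interval.

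**Adjusting for the baseline score.** Take SD 1 at both times, complete follow-up and three arms of 15, so 45 − 3 = 42 error degrees of freedom.

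- Change contrast: variance = 2(1 − r) × 2/15.
- Baseline-adjusted contrast (ANCOVA): variance = (1 − r²) × (2/15) × (1 + 1/40), where 40 = 42 − 2 reflects estimation of the slope.
- Ratio = 1.025 × (1 + r)/2.

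At r = 0.5 the variances are 0.1333 and 0.75 × 0.1333 × 1.025 = 0.1025, a ratio of 0.769. The 95% half-widths use t on 42 and 41 degrees of freedom.

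| r | Variance ratio | Half-width, change (SD) | Half-width, ANCOVA (SD) |
|---|---|---|---|
| 0.3 | 0.666 | 0.872 | 0.712 |
| 0.5 | 0.769 | 0.737 | 0.647 |
| 0.7 | 0.871 | 0.571 | 0.533 |
| 0.93 | 0.989 | 0.276 | 0.274 |

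The ratio reaches 1 at r = 2/1.025 − 1 = 0.951.

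**Sensitivity.** With 12 per arm (an assumed 20% loss) the factor is 1 + 1/31 and the ratios are 0.671, 0.774, 0.877 and 0.996. If the follow-up SD is k times the baseline SD, the ratio is 1.025 × k²(1 − r²)/(k² + 1 − 2rk). Over the same r this gives 0.515 to 0.643 for k = 0.8 and 0.804 to 1.005 for k = 1.25. The maximum at 15 per arm is 1.025, when the true slope rk equals 1.

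**Selecting by association with treatment.** The plan gives no list or threshold, so both are assumed: a one-way F screen at 5% or 20%, no true effect, change as the outcome, 40,000 simulated trials per setting. Entries are variance ratios to the unadjusted change, for the 5% / 20% screen.

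| r | Always adjust for baseline | Baseline the only candidate | Baseline plus seven non-prognostic candidates | Two of the seven prognostic (30% of residual variance) |
|---|---|---|---|---|
| 0.3 | about 0.67 | 0.931 / 0.826 | 0.972 / 0.921 | 0.936 / 0.815 |
| 0.5 | about 0.77 | 0.959 / 0.887 | 0.992 / 0.973 | 0.950 / 0.857 |
| 0.7 | about 0.87 | 0.976 / 0.936 | 1.014 / 1.029 | 0.963 / 0.893 |
| 0.93 | about 0.99 | 0.997 / 0.995 | 1.033 / 1.090 | 0.978 / 0.931 |

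The share of the gain recovered is (1 − ratio under the rule)/(1 − ratio when always adjusting). With baseline as the only candidate at r = 0.3 and a 5% screen, that is 0.069/0.337 = 20%. For r from 0.3 to 0.7 this list recovers about a fifth at 5% and half at 20%. With seven non-prognostic candidates added, the shares are 8% / 24% at r = 0.3, about 4% / 12% at r = 0.5, and none at r = 0.7. With two prognostic candidates they are 19% / 55%, 22% / 62% and 29% / 84% at r = 0.3, 0.5 and 0.7. A fixed model with baseline and those two covariates has ratios 0.489, 0.567, 0.642 and 0.728 at the four values of r.

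**Child age for CDI and DECA.** With age-score correlation ρ (assumed), the ratio to an arm-only comparison is 1.025 × (1 − ρ²): 0.933, 0.769 and 0.523 at ρ = 0.3, 0.5 and 0.7, and 1.025 at ρ = 0. Break-even is ρ = √(1 − 1/1.025) = 0.16.

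**The case against.** The outcomes are only exploratory, in a pilot sized by funds and time, and the change contrast is valid. At r = 0.5 the half-width moves from 0.74 to 0.65 SD, and neither is a firm basis for powering a later trial. That stands, and it limits the weight of the point.

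The gain depends on an r that the documents do not supply; at 0.93 it is about 1%. That also stands. But 0.93 is not an 8-week figure for the Read subscale, and PSI-SF has no figure at all.

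The words in 6.3 can be read more kindly: a confounder is normally related to outcome, and the rule leaves room for judgement. This shows an intention to adjust. It fixes no covariate for these endpoints, and the only stated criterion remains association with treatment.

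Section 6.3 item (3) says "The primary source of bias will arise after randomization from dropout and loss to follow-up". Among participants with follow-up scores, imbalance need not be pure chance. This qualifies the argument, but the plan does not tie its covariate rule to dropout.

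The simulated screens are not the plan's own rule. The rule was less precise than the fixed model holding the prognostic covariates in all 24 combinations, but that is close to guaranteed. With two prognostic candidates at r = 0.93 the rule (0.98 / 0.93) beat adjustment for baseline alone (0.99). The simulation shows only how far the result depends on choices left open.

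Finally, the closed-form ratios omit the site term. In a simulation with four sites, half-widths for arm, baseline and site were 0.713, 0.649, 0.535 and 0.275, against 0.869, 0.735, 0.570 and 0.275 for the change. The gain survives at r from 0.3 to 0.7 and vanishes at 0.93.

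**Conclusion.** The concern holds. Fixed adjustment for the baseline score would cut the variance of the StimQ-Read and PSI-SF contrasts by about 33%, 23%, 13% or 1% at r = 0.3, 0.5, 0.7 or 0.93, assuming 15 per arm, complete follow-up and equal variances. With unequal variances the gain can be larger or disappear; the worst case is 2.5% more variance. What the present rule loses cannot be stated without its candidate list and threshold.

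For CDI and DECA, age adjustment helps if the age-score correlation exceeds about 0.16. It helps less if age-standardised scores are used, which the plan does not say.

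This should be changed because it is a modest improvement using data already collected. It does not touch the primary endpoints and does not make 15 per arm precise.

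**What to change.** In 6.4.3.1, state that the Group 2 v 1 and Group 3 v 1 contrasts for StimQ-Read and PSI-SF total come from a linear model of the follow-up score on arm, the baseline value of the same measure, and site, with 95% confidence intervals. Modelling the change with the same covariates gives the same arm contrast. For CDI and DECA, use arm, site and child age at baseline. In 6.3 item (2), replace selection by association with treatment with this fixed set, plus any other covariates named in advance for expected prognostic value. Site is included to match the stratified randomisation, not for a demonstrated gain in precision.

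The cost is wording, settled before outcome data are seen. One baseline (or age) term and 2 to 3 site terms (3 to 4 practices) use 3 to 4 of the 42 error degrees of freedom, leaving 38 to 39. In simulation for CDI and DECA with four sites, the mean half-width was 0.733 SD with arm only, 0.737 with arm and site, and 0.648 with arm, site and age at correlation 0.5. If age were unrelated to the score, it would be 0.746 instead of 0.735.

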5.1.2 Other Evaluations, Measures

At the start of phase 2, following written informed consent, participant families will complete a baseline visit. In the event that the visit cannot be completed in person, study procedures may be conducted virtually online through REDCap. Measures of demographic and biological variables (child age, sex, race/ethnicity, family income, maternal education level, and family structure), parenting stress, and the home reading environment will be collected by research staff blinded to randomization assignment at this visit (See Appendix 2).

The Read subscale of the StimQ is a validated 14-item parent self-report questionnaire designed to measure of the home reading environment, at baseline and follow-up for children ages 5 to 72 months of age.²³ The StimQ contains 4 subscales (availability of learning materials, reading, parental involvement in 1 developmental advance, parental verbal responsiveness) and is available in English and Spanish. Internal consistency (Cronbach $\alpha=0.88-0.93$) and test-retest reliability (ICC=0.93) of the StimQ is excellent, and it correlates well ($r=0.55$) with the IT-HOME Inventory, another measure of the home environment.⁷⁸ Poverty will be assessed by examining family income (<100% of the Federal Poverty Level) and maternal education status (\leq High School). Parenting stress will be measured at baseline and at follow-up 2 months later using the Parenting Stress Index-Short Form (PSI-SF).²⁴

Parenting Stress Index-Short Form (PSI-SF): Baseline and follow-up. The PSI-SF is a validated 36-item scale that measures parenting stress. It has been shown to have excellent internal consistency and to be positively associated with maternal psychological distress. Scores on the PSI-SF correlate well with the full PSI. The total score will be used.

MacArthur Communicative Development Inventory (CDI): 2-month follow-up. CDI is a validated parent-report scale of early language development which captures important information including language comprehension, production and grammar.²⁶

Devereux Early Childhood Assessment (DECA): 2-month follow-up. DECA is a validated 33-item parent report of socio-emotional problems used to identify children at risk for language deficits.²⁵

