8.1.2 Blinding

Allocation concealment (blinding of the treatment assignment) will be implemented using sealed, opaque envelopes, along with stratification, and randomly permuted blocks of unequal sizes (to prevent providers and patients from manipulating the randomization). Participants will not be blinded to their treatment assignment. However, research will be blinded to treatment assignment when collecting study data.

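### CDI is measured once, at follow-up, in children aged about 8 to 27 months, but child age enters its analysis only if a check of association with treatment calls for it; if the score is not age-standardised, precision is lost.

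*Combined protocol and SAP*

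**What the plan says.** All places are in the combined protocol and SAP.

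- **Timing.** Table 1 and sections 3.1.3, 4.2.1 and 5.1.2 place CDI and DECA at follow-up only. StimQ-Read and PSI-SF are also taken at baseline and are analysed as changes.
- **Analysis.** Section 6.4.3.1 (secondary outcomes) compares "mean CDI and DECA scores between groups using standard inferential statistics and intention-to-treat analysis". It names no covariate and no score type. It adds that effect sizes for Groups 2 and 3 against Group 1 will help to power later studies.
- **Scoring.** Section 5.1.2 gives a scoring rule, "The total score will be used", for the PSI-SF alone. It describes CDI as covering comprehension, production and grammar.
- **Covariates.** Section 6.3, clause (1), says "Stratification will control for imbalance not controlled by design". Clause (2) says "Additional potential confounders will be evaluated for any residual association with treatment and included in model as needed". Neither names age.
- **Stratification.** Section 3.1.2: "participants will be stratified by site and randomized 1:1:1 to receive one of the 3 AH interventions". Section 8.1.2 says only "along with stratification, and randomly permuted blocks of unequal sizes" and gives no factor; section 3.2 is the same. Site is therefore the only factor named.
- **Age data.** Section 3.1.3: "parents will complete a measure of demographics (child and parent age". Section 5.1.1 lists date of birth. Section 6.4.1: "Descriptive statistics for demographic, home reading environment, and parenting stress measured at baseline will be examined across the three groups". That would display an age imbalance, but no analysis follows from it.

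**The concern.** A language measure that spans comprehension to grammar can be expected to rise with age over this range unless it is scored against age norms. With no baseline CDI, age is the obvious available predictor of the follow-up score.

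In a randomised comparison, a covariate earns its place by predicting the outcome. Clause (2) of section 6.3 selects on association with treatment instead, and randomisation makes any such association a matter of chance. Age could therefore be left out of the CDI model however well it predicts the score, and the choice would be made after the data are seen.

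If the score is not age-standardised, two things follow. First, age variance stays in the error term and widens every interval. Second, in a trial that happens to have an age gap between arms, that gap is carried into the estimated effect. Both matter mainly because these exploratory effect sizes are intended for planning later trials.

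**Working it through.** **Plan's own figure.** Section 6.4.2 gives 3 × 15 = 45 for Phase 2, set by funds and time. It states no alpha, power, SD or effect size, so there is no power figure to reproduce.

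**Inputs from the documents.** Entry age 6–24 months (3.4.1); follow-up at 8–12 weeks (Table 1); 15 per arm (6.4.2); 3–4 sites (3.3.2).

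**Assumptions, not in the documents.** Ages uniform over the entry range; linear age–score relation with R² of 0.3, 0.5 or 0.7; no site effect; all 45 followed up; two-sided 5% test; 80% power.

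**1. Age at measurement.** 6 months + 8 weeks = 7.8 months; 24 months + 12 weeks = 26.8 months.

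**2. Precision.** The detectable difference is δ × √(2/15) × √(1 − R²) × SE inflation. Here δ is the noncentrality giving 80% power (2.87 on 42 df), and the inflation is the average cost of fitting age and site (1.014 with 3 sites, 1.017 with 4).

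| Model | R² = 0 | 0.3 | 0.5 | 0.7 |
|---|---|---|---|---|
| Unadjusted, 42 df | 1.05 | 1.05 | 1.05 | 1.05 |
| Age + 3 sites, 39 df | 1.07 | 0.89 | 0.75 | 0.58 |
| Age + 4 sites, 38 df | 1.07 | 0.90 | 0.76 | 0.59 |

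Units are SDs of the unadjusted score. The R² = 0 column also represents an age-standardised score: there is then no gain and a very small loss.

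**3. Chance imbalance.** Age SD = 18/√12 = 5.20 months. SE of the difference in mean age between two arms = 5.20 × √(2/15) = 1.90 months. The chance of a gap over 2 months is 29% (17% if the age SD is 4, 7% if it is 3). A 2-month gap shifts the unadjusted difference by 2 × √R²/5.20 = 0.21, 0.27 or 0.32 SD. The unadjusted 95% half-width is t(0.975, 42) × √(2/15) = 0.74 SD.

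**4. What the section 6.3 check does about it.** The documents give no threshold, so several readings were simulated with no true effect. The screens are ANOVA tests of age across the three arms. The table gives the rejection rate in trials with an age gap over 2 months.

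| How age enters | Null rejection, R² 0.3–0.7 |
|---|---|
| Never | 10%–16% |
| If p < 0.05 for age | about 8%–11% |
| If p < 0.2 for age | about 6% |
| Always | about 5% |

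If age is never fitted, the remaining trials reject in 2.8%, 1.6% or 0.5% of cases, and the overall rate is 5%. With a screen, the overall rate is at or below 5%.

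**5. Standardising SD.** Once age is fitted, the residual SD is √(1 − R²) of the raw SD. The same difference is then 1/√(1 − R²) = 1.20, 1.41 or 1.83 times larger in residual-SD units than in raw-SD units. A later team needs to know which was used.

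**The case against.** The strongest reply is that section 6.3 already has a covariate rule and that a chance age gap is just what it looks for. It also speaks of potential confounders, a term that normally implies a relation to outcome. Much of this stands. The 10%–16% figure applies only if the rule never brings age in, and a lenient screen removes most of the excess. What the rule does not recover is precision in the many trials where age happens to be balanced and is therefore left out.

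A second reply is that no text says the CDI score is raw, that the appendix may settle it, and that the R² values are assumed. This stands too, so the point is conditional.

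Third, these are exploratory outcomes in a pilot, where 15 per arm limits precision more than any covariate choice. That is right and sets the weight.

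A reader might infer more than the documents support:
- *That the planned comparison is biased or has inflated type I error.* Randomisation keeps it unbiased on average, and the overall error rate is at or below 5%.
- *That DECA shares the problem equally.* The documents give no reason to expect an age trend in DECA.
- *That the scores are raw.* The documents do not say so.

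**Conclusion.** The point holds for CDI, conditionally and at minor weight. As written, the plan can leave out a collected and probably strong predictor of a follow-up-only score because its inclusion rule looks at the wrong association. If the analysed score is not age-standardised, the main loss is precision: about 1.05 SD detectable against 0.89 to 0.58 SD, on the assumed R² of 0.3 to 0.7 and complete follow-up. Chance imbalance is secondary and only partly handled by the section 6.3 check, to a degree that depends on an unstated threshold. If the score is age-standardised, fitting age gains nothing. The textual gap rests on no assumption; its size does. The primary feasibility and acceptability conclusions do not change.

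**What to change.** In section 6.4.3.1:

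1. State whether the analysed CDI score is age-standardised. If the appendix already fixes this, cite it.
2. If it is not, analyse CDI in a linear model on arm, child age at follow-up and site, fitted whatever age imbalance is observed. If it is, fit arm and site only.
3. Apply the same rule to DECA only if its analysed score is not age-standardised.
4. Report adjusted differences for Group 2 versus 1 and Group 3 versus 1 with 95% CIs, and state whether the raw or residual SD standardises the effect sizes meant for planning.

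In section 6.3, exempt age from the association-with-treatment check for CDI, and for DECA where step 3 applies.

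**Cost.** Wording only, with no new data: date of birth and child age are collected, and site is already a stratification factor. The model with age uses 3 to 4 degrees of freedom (42 residual df fall to 39 with 3 sites or 38 with 4). If neither covariate predicts the score, standard errors widen by about 1.4% to 1.7%. The age term assumes a roughly linear trend over the range, which should be checked when the model is fitted.
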